6.4. Vital Signs

Vital signs will include blood pressure, pulse, and oral or tympanic body temperature. For orthostatic vitals, blood pressure and pulse should be collected or recorded while the subject is in the supine and standing position at the following visits: Baseline Day 1 (V2), Month 6 (V6), Month 12 (V8) or early termination visit. Blood pressure and pulse should be collected while the subject is sitting at all other visits.

The following vital signs endpoints will be determined:

- The maximum decrease and increase from baseline over all measurements taken postdose for supine and standing systolic and diastolic blood pressures;
- Postural differences (supine – standing) for systolic and diastolic blood pressures and for pulse rate.

The maximum increase from baseline will be calculated by first subtracting the baseline value from each post dose measurement to give the change from baseline. The maximum of these values over the respective period will then be selected, except in the case where a subject does not show an increase. In such an instance, the minimum decrease should be taken.

Similarly, the maximum decrease from baseline will be determined by selecting the minimum value of the changes from baseline. In cases where a subject does not show a decrease, the minimum increase should be taken.

6.5. Electrocardiogram (ECG)

Single 12 lead ECGs will be recorded at Baseline Day 1 (V2), and collected at Month 3 (V5), Month 6 (V6), Month 9 (V7) and Month 12 (V8), or at early termination, and may be performed at Unscheduled Visit(s).

Subjects must rest in the supine position for at least 10 minutes before the ECG recording is started. The ECG should be recorded during the period of rest required before blood collection and the measurements of orthostatic blood pressure and pulse. A qualified physician will review the ECGs and any clinically important finding will be recorded on the appropriate CRF. The investigator is responsible for providing interpretation of all ECGs. The results will include heart rate (RR), PR interval, QRS interval, QT interval, and correct QT (QTc) interval, and assessment of rhythm and morphology. If necessary (eg, suspected QTc prolongation), a manual reading of the ECG data will be performed.

If not supplied, QTcF will be derived using Fridericia's heart rate correction formula:

$$\text{QTcF} = \text{QT} / (\text{RR})^{2/3} \text{ where RR} = 60/\text{HR} \text{ (if not provided).}$$

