7.7.7. Electrocardiogram (ECG)

ECGs should be collected at times specified in the STUDY PROCEDURES Section of this protocol. Single 12-lead ECGs will be recorded or collected at on Baseline Day 1 (V2),

Month 3 (V5), Month 6 (V6), Month 9 (V7), Month 12 (V8) or at early termination, and may be performed at Unscheduled Visit(s).

Subjects must rest in the supine position for at least 10 minutes before the ECG recording is started. The ECG should be recorded during the period of rest required before blood collection and the measurements of orthostatic blood pressure and pulse. A qualified physician will review the ECGs and any clinically important finding will be recorded on the appropriate CRF. The investigator is responsible for providing interpretation of all ECGs. The results will include heart rate, PR interval, QRS interval, QT interval, and QTc interval, and assessment of rhythm and morphology. If necessary (eg, suspected QTc prolongation), a manual reading of the ECG data will be performed.

In some cases, it may be appropriate to repeat abnormal ECGs to rule out improper lead placement as contributing to the ECG abnormality. It is important that leads are placed in the same positions each time in order to achieve precise ECG recordings. If a machine-read QTc value is prolonged, as defined above, repeat measurements may not be necessary if a qualified physician's interpretation determines that the QTc values are in the acceptable range.

All ECGs will also be centrally read. Instructions for transmission of ECGs to the vendor will be provided in the ECG vendor manual.

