9.5.1. Electrocardiogram (ECG) Analysis

Changes from baseline for the ECG parameters QT interval, heart rate, QTc interval, PR interval and QRS interval will be summarized by treatment and time. The number (%) of subjects with maximum post-dose QTc values and maximum increases from baseline in the following categories will be tabulated by treatment:

Table 7. Safety QTc

	Borderline (msec)	Prolonged (msec)
Absolute Value	>=450 - <480	>=480
Absolute Change	30-<60	>=60

In addition, the number of subjects with corrected and uncorrected QT values >=500 msec will be summarized.

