8.3.10. ECG

Absolute values and changes from baseline in PR, QT, QRS, heart rate (RR) and QTcF will be summarized, time postdose and day using sponsor reporting standards. Tables will be paged by parameter.

ECG endpoints and changes from baseline (QTcF, PR, QRS) will also be summarized descriptively by using categories as defined in [Appendix 1](#) (for QTc these correspond to ICH E14¹). Numbers and percentages of subjects meeting the categorical criteria will be provided. All planned and unplanned postdose timepoints will be counted in these categorical summaries. All values meeting the criteria of potential clinical concern will be listed.

Listings of subjects with any single postdose value ≥ 500 msec will also be produced for QTcF.

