Appendix 1. Categorical Classes for ECG and Vital Signs

Categories for QTcF

QTcF (ms)	450≤ max. <480	480≤ max. <500	max. ≥500
QTcF (ms) increase from baseline	30≤ max. <60	max. ≥60	

Categories for PR and QRS

PR (ms)	max. ≥300	
PR (ms) increase from baseline	Baseline >200 and max. ≥25% increase	Baseline ≤200 and max. ≥50% increase
QRS (ms)	max. ≥140	
QRS (ms) increase from baseline	≥50% increase	

Categories for Vital Signs

Systolic BP (mm Hg)	min. <90	
Systolic BP (mm Hg) change from baseline	max. decrease ≥30	max. increase ≥30
Diastolic BP (mm Hg)	min. <50	
Diastolic BP (mm Hg) change from baseline	max. decrease ≥20	max. increase ≥20
Supine pulse rate (bpm)	min. <40	max. >120
Standing pulse rate (bpm)	min. <40	max. >140

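### SAP 6.5 prints Fridericia's correction with exponent 2/3 instead of 1/3, so any QTcF derived by that rule is wrong unless heart rate is 60 bpm

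*SAP*

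**What the plan says.** SAP 6.5 states: "If not supplied, QTcF will be derived using" Fridericia's formula. The equation that follows is QTcF = QT/(RR)^(2/3), with RR taken as 60/HR when it is not provided.

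SAP 8.3.10 then uses the variable in three ways:

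- QTcF values and changes from baseline are summarised.
- They are also put into categories: "ECG endpoints and changes from baseline (QTcF, PR, QRS) will also be summarized descriptively by using categories as defined in" Appendix 1. The absolute bands there are 450 to <480, 480 to <500 and ≥500 ms. The row "QTcF (ms) increase from baseline" has bands 30 to <60 and ≥60 ms.
- There is a listing: "Listings of subjects with any single postdose value ≥ 500 msec will also be produced for QTcF".

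Two protocol provisions bear on the reach of the problem. Section 7.7.7 says "All ECGs will also be centrally read". Section 9.5.1 says "the number of subjects with corrected and uncorrected QT values >=500 msec will be summarized".

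**The concern.** The method named and the equation printed are not the same, so a programmer cannot follow both. Fridericia's correction divides QT by the cube root of RR. An exponent of 2/3 over-corrects, so the result still depends on heart rate, which is the dependence the correction is meant to remove.

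Assessment of ECG parameters is listed under the primary endpoint (Protocol 2.2 and 9.2.1; SAP 6.1) and is summarised descriptively. Where the fallback is used, normal values can enter a prolongation band and prolonged values can leave one. A shift in heart rate alone can look like a change in QTc or cancel a real one. The extension has no concurrent control group, so the change from baseline carries much of the interpretation.

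**Working it through.** **Inputs.** The exponent 2/3 and RR = 60/HR come from SAP 6.5. The bands and the 500 ms cut-off come from SAP Appendix 1 and 8.3.10. Fridericia's exponent, 1/3, is the definition of the method the SAP names. All QTcF and heart-rate values below are illustrative assumptions, because the documents give none.

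**Could 2/3 be another recognised form?** Bazett's exponent is 1/2, so it is not that. RR in milliseconds does not rescue it either: QT 380 ms with RR 800 ms gives 380/800^(2/3) = 4.4.

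**Relation between the two.** If the correct value is QTcF = QT/RR^(1/3), then QT = QTcF × RR^(1/3). The value as printed is therefore

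QT/RR^(2/3) = QTcF × RR^(-1/3) = QTcF × (HR/60)^(1/3).

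The two agree only at 60 bpm.

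| Heart rate (bpm) | (HR/60)^(1/3) | Error |
|---|---|---|
| 50 | 0.941 | -5.9% |
| 60 | 1.000 | 0 |
| 70 | 1.053 | +5.3% |
| 75 | 1.077 | +7.7% |
| 80 | 1.101 | +10.1% |
| 90 | 1.145 | +14.5% |

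**False entry into a band**

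- True 410 ms at 75 bpm: 410 × (75/60)^(1/3) = 441.7 ms. At 80 bpm: 410 × (80/60)^(1/3) = 451.3 ms, inside 450 to <480. The crossing point is 60 × (450/410)^3 = 79.3 bpm.
- True 480 ms at 68 bpm: 480 × (68/60)^(1/3) = 500.4 ms, which enters the ≥500 ms listing.

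**Loss from a band, at 50 bpm**

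- True 500 ms: 500 × 0.941 = 470.5 ms, so it leaves the SAP listing. Uncorrected QT is 500/0.941 = 531.3 ms, so the uncorrected count in Protocol 9.5.1 still catches it. That count catches every true QTcF ≥500 ms below 60 bpm, because there QT exceeds QTcF.
- True 455 ms: 455 × 0.941 = 428.2 ms, in no absolute band. Uncorrected QT is 455/0.941 = 483.5 ms, below 500, so the uncorrected count does not catch it.
- The printed value is below 450 for any true QTcF under 450/0.941 = 478.2 ms, and QT is below 500 for any true QTcF under 500 × 0.941 = 470.5 ms. True values from 450 to about 470 ms therefore escape both.

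**Change from baseline, both values derived by the fallback**

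- Constant true 410 ms, heart rate 70 to 86 bpm: 410 × [(86/60)^(1/3) - (70/60)^(1/3)] = +30.7 ms, a false entry in the 30 to <60 band.
- True rise of 35 ms (410 to 445), heart rate 75 to 65 bpm: 445 × (65/60)^(1/3) - 410 × (75/60)^(1/3) = 457.0 - 441.7 = +15.4 ms before rounding the terms, so the rise leaves that band.

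**Change from baseline, correct supplied baseline and derived post-dose value**

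- Constant true 410 ms, post-dose heart rate 80 bpm: 451.3 - 410 = +41.3 ms, again a false entry.

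**The case against.** The strongest reply is that this is a misprint in a line that may never be used. The results listed in Protocol 7.7.7 and SAP 6.5 include a QTc interval, and all ECGs are read centrally. The method is named, so a program written from the name would be right. SAP 8.3.10 also defers to sponsor reporting standards, which are not in the documents. The output is descriptive, the stopping criteria in Protocol 3.1 do not use QTcF, and physicians review the ECGs directly. The exponent was read from a PDF by a program. The worked examples use chosen values, some close to a cut-off.

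Much of this limits the reach of the error and stands as a limit. The share of ECGs affected is unknown and could be zero, and the documents do not show that any value was computed wrongly. Table 7 in Protocol 9.5.1 bands an unspecified QTc. If a reader's own QTc filled that table, the 455 ms example would show there, although the SAP's categories are written for QTcF.

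None of it makes the printed rule correct. Neither document says that the reported QTc is Fridericia-corrected or that the central reader supplies QTcF. The SAP is the specification for the derivation, and followed literally it gives wrong values. The extracted text shows 2/3 plainly, with no sign of corruption.

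**Conclusion.** The formula is wrong as written and must be corrected. Each QTcF derived from it is off by the factor (HR/60)^(1/3), from about -6% at 50 bpm to +14.5% at 90 bpm. At ordinary resting rates that is enough to move values across the 450, 480 and 500 ms cut-offs and the 30 ms change cut-off, in either direction.

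This rests on the exponent having been read correctly from the SAP page and applies only to ECGs for which QTcF was not supplied. How many those are cannot be estimated from the documents. Supplied values are not themselves affected, but a change from baseline that pairs a supplied value with a derived one is.

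**What to change.** In SAP 6.5, print QTcF = QT/(RR)^(1/3), with RR in seconds = 60/HR. Check the original SAP page and the analysis program for the exponent, and re-derive any value found to have been computed with 2/3, together with the tables and listing that use it. State whether the central reader supplies QTcF, and report the number of QTcF values that were derived.

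The cost is a one-line SAP correction and a program check, plus a rerun of the ECG outputs only if 2/3 was used. No data collection or clinical procedure changes.

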6.6. Suicidal Ideation and Behavior (SIB) Assessments During the Clinical Trial

The Columbia Suicide Severity Rating Scale (C-SSRS) is an interview-based rating scale to systematically assess suicidal ideation and suicidal behavior³³. The scale should be administered to the subject by an individual with appropriate training, who has also taken the specific rater training for the scale, which will be provided by an agent of the sponsor prior to the study start. This scale will be recorded or administered ("since Last Visit") at each study visit from Baseline Day 1 (V2) to Follow-up visit (V9), including early termination.

C-SSRS responses will be mapped to the Columbia Classification Algorithm of Suicide Assessment (C-CASA). (See [Appendix 2](#)).

The following 3 endpoints are key endpoints for suicidality data analysis and evaluation:

- Suicidal Behavior;
- Suicidal Ideation;
- Suicidal Behavior or Ideation.

Suicidal behavior: A subject is said to have suicidal behavior if the subject has experienced any of the following events (C-CASA event codes 1-3):

- Completed suicide;
- Suicide attempt; or
- Preparatory acts toward imminent suicidal behavior.

Suicidal ideation: Any observed suicidal ideation maps to a single C-CASA category. The C-SSRS, for example, includes five ideation questions (that map to C-CASA category 4) with increasing severity.

Subjects with new onset suicidality: A subject will be considered to have a new onset of suicidality if the subject reported no ideation and no behavior at the baseline assessment (note that self-injurious behavior, no suicidal intent [C-CASA code 7] is not considered to be suicidal ideation or behavior) and reported any behavior or ideation post-baseline. Data observed at screening is not considered in the definition of new onset.

Subjects with worsening suicidality relative to baseline: A subject will be considered to have a worsening of suicidality if the subject moved to a lower numbered C-CASA category (observed in categories 1-4) than was reported at baseline. Movement within C-CASA categories 5-9 would not be considered worsening. In addition, worsening will be considered within the suicide ideation C-CASA category 4 if there is an increase in severity identified in the C-SSRS which captures additional granularity on suicide ideation. A subject who reports only ideation at baseline and who reports any behavior post-baseline is considered to have worsened. Data observed at screening is not considered in the definition of worsening.

6.7. CCI

(CCI)

CCI

CCI

CCI [REDACTED]

[REDACTED]

6.8. Efficacy Endpoint(s)

Secondary Endpoints:

- *Change from baseline in the Total Motor Score (TMS) assessment of the Unified Huntington Disease Rating Scale (UHDRS) after 6 and 12 months of treatment.* The score decreases indicate improvement.
- *Change from baseline in the Total Maximum Chorea (TMC) score of the UHDRS after 6 and 12 months of treatment.* The score decreases indicate improvement.
- *Clinical Global Impression-Improvement score after 6 and 12 months of treatment.* The score decreases indicate improvement.

CCI [REDACTED] :

CCI [REDACTED] :

- CCI [REDACTED]

CCI [REDACTED] :

- CCI [REDACTED]

- CCI [REDACTED]

CCI [REDACTED] :

- CCI [REDACTED]

CCI [REDACTED] :

- CCI [REDACTED]

- CCI [REDACTED]
- CCI [REDACTED]

CCI [REDACTED]:

- CCI [REDACTED]
- CCI [REDACTED]
- CCI [REDACTED]
- CCI [REDACTED]
- CCI [REDACTED].

6.8.1. Unified Huntington's Disease Assessment Scale (UHDRS)

In this study four subscales of the UHDRS will be administered to the subject by a trained certified rater of the site investigational staff (clinician): the Total Motor Score (TMS), CCI [REDACTED] (CCI, CCI [REDACTED] CCI [REDACTED].

The UHDRS is a clinical rating scale which has been developed by the Huntington Disease Study Group (HSG) to provide a uniform assessment of the clinical features and course of HD. The UHDRS scale has undergone reliability and validity testing and has been used as a major outcome measure in controlled clinical trials and observational studies. CCI [REDACTED]

CCI [REDACTED].

The total motor score (TMS) will be recorded from study A8241021 at Baseline Day 1 (V2) visit, and will be administered at each study visit from Week 2 (V3) to Month 12 (V8) and in case of early termination.

The TMS assesses motor features of HD with standardized ratings of oculomotor function, dysarthria, chorea, dystonia, gait, and postural stability. Some items (such as chorea and dystonia) require grading each extremity (face, bucco-oral-lingual, and trunk) separately. Eye movements require both horizontal and vertical grades. The total motor impairment scores is the sum of all the individual motor ratings, with higher scores indicating more severe motor impairment than lower scores.

The Total Maximum Chorea (TMC) is a subset of the TMS assessment. It is composed of the scoring of 7 chorea assessments (face, orobuccolingual, trunk, right and left upper extremities, right and left lower extremities). Each assessment is rated from 0 to 4 (absent to prolonged). The TMC score can be derived from the TMS score at visits at which the TMS is collected.

CCI

CCI

CCI

CCI

Administration and scoring guidelines will be provided to the investigator site during rater training sessions prior to initiation of the study.

6.8.2. CCI [REDACTED] (CCI)

CCI

CCI

.

6.8.3. CCI

CCI

CCI

CCI

• CCI

CCI

CCI

CCI

CCI

CCI

- CCI [REDACTED] (CCI [REDACTED]).

CCI [REDACTED] (CCI [REDACTED]).

CCI [REDACTED] (CCI [REDACTED])

CCI

[REDACTED]

- CCI [REDACTED]

CCI [REDACTED] (CCI [REDACTED])

CCI

CCI [REDACTED] :

- CCI [REDACTED]

- CCI (CCI).

CCI (CCI)

CCI

CCI

1. CCI

2. CCI

CCI

CCI

CCJ

6.8.4. CCI

CC1

[figure not shown]
CCI

CCI

- CCI
- [REDACTED]
- [REDACTED]
- [REDACTED]
- [REDACTED]
- [REDACTED]

CCI

- CCI
- [REDACTED]
- [REDACTED]
- [REDACTED]

CCI

CCI

CCI

- CCI

6.8.5. Clinical Global Impression of Severity/Improvement (CGI-S/CGI-I)

The CGI-S/CGI-I is a global measure of severity of illness (CGI-S) and improvement or change (CGI-I) based on the clinician's assessment of all available clinical data obtained from interviewing the subject.

The CGI-S consists of a single 7-point rating score of illness severity that is based on how ill the subject is relative to other subjects he/she has had experience with. Raters select one response based on the following question, "Considering your total clinical experience with this particular population, how ill is your subject at this time?" Scores are: 1, Normal, not ill at all; 2, Borderline ill; 3, Mildly ill; 4, Moderately ill; 5, Markedly ill; 6, Severely ill; or 7, Among the most severely ill subjects.

The CGI-I consists of a single 7-point rating of total improvement or change from baseline CGI-S, regardless of whether or not the change is due entirely to drug treatment. Raters select one response based on the following question, "Compared to your subject's condition at the beginning of treatment, how much has your subject changed?" Scores are: 1, Very much improved; 2, Much improved; 3, Minimally improved; 4, No change; 5, Minimally worse; 6, Much worse; or 7, Very much worse.

The CGI-S/CGI-I rater can have access to all clinical information related to subject severity and change, and does not need to be independent of other assessments. However, the rater who assesses the initial CGI-S should be the clinician who rates overall change via the CGI-I during the study.

The CGI-S will be performed at Baseline Day 1 (V2). The CGI-I will be administered at Month 6 (V6), Month 12 (V8), and in case of early termination. This assessment will be administered by a trained rater from the site investigational team (eg, clinician).

6.8.6. CCI

CCI

CCI :

- CCI

6.8.7. [REDACTED]

CCI

[REDACTED]

[REDACTED]

[REDACTED]

[REDACTED]

CCI [REDACTED]

6.9. CCI [REDACTED]

6.10. CCI [REDACTED]

CCI [REDACTED]

6.11. PD Endpoints

None.

6.12. CCI [REDACTED]

CCI [REDACTED]

[REDACTED]

[REDACTED]

[REDACTED]

[REDACTED]

7. HANDLING OF MISSING VALUES

For the analysis of safety endpoints, the sponsor data standard rules for imputation will be applied.

For scales used in this study (eg, UHDRS), no missing response will be allowed in the study. A query will be sent to the site if there is missing response.

Concentrations below the limit of quantification

In all data presentations (except listings), concentrations below the limit of quantification (BLQ) will be set to zero. (In listings BLQ values will be reported as “<LLQ”, where LLQ will be replaced with the value for the lower limit of quantification).

Deviations, missing concentrations and anomalous values

In summary tables and plots of median profiles, statistics will be calculated having set concentrations to missing if 1 of the following cases is true:

1. A concentration has been collected as ND (ie, not done) or NS (ie, no sample);
2. A deviation in sampling time is of sufficient concern or a concentration has been flagged anomalous by the pharmacokineticist.

Note that summary statistics will not be presented at a particular time point if more than 50% of the data are missing.

8. STATISTICAL METHODOLOGY AND STATISTICAL ANALYSES

8.1. Statistical Methods

The Safety population will be used in the analyses of the safety data. The FAS analysis set will be utilized for efficacy endpoints.

All efficacy endpoints will be summarized descriptively at each visit for all subjects as well as separated by three groups (ie, from PF 20mg, from PF 5mg, and from Placebo). 90%CI will be provided for the mean. Plots with the mean over time with 90%CI will be generated for all subjects as well as by three different groups.

Baseline and change from baseline for each efficacy endpoints will also be summarized descriptively at each visit for all subjects as well as separated by three groups. Plots with mean change from baseline over time with 90%CI will be generated for all subjects as well as by three different groups.

Due to the unexpected termination of the study, any early termination visits (ET), which occurred on and after Dec. 16th, 2016, will not be included in the summary tables and plots. These data will be listed only.

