Visit Number	V1	V2	V3	V4	V5	V6	V7	V8	V9
Study Day		Day 1	Day 14	Day 28	Day 91	Day 182	Day 273	Day 365	Day 372 to 379
CCI		CCI				CCI		CCI	
CCI									
ANC and WBC Review ¹⁷	X	(X) ⁸	X	X	X	X	X	X	X
Site Eligibility Review ⁶ Sponsor Eligibility Verification ¹⁸ and Documentation of Confirmation	X X	X							
Randomization ¹⁹		X							
CCI 20									
CCI CCI						GGI		ec.	
		GGI							
Diameter live		V							
Dispense dosing diary Dispense study drug for outpatient dosing		X X	X	X	X	X	X		
Subject instruction on outpatient dosing		Λ	Λ	Λ	Λ	Λ	Λ		
from blister packs/bottles, dosing diary use and reporting AEs and SAEs.		X							
Assess compliance based on observation of blister packs, pill counts, review dosing diary			X	X	X	X	X	X	
Collect dosing diary				X					

Footnotes:

- 1. All visits windows are relative to the V2 Baseline Day 1 visit date.
- 2. Screening visit will take place during the Week 19 Visit for study A8241021.
- 3. Baseline Day 1 activities will take place during Week 26 Visit for Study A8241021.
- 4. In case of Early Termination between Baseline and Day 14 (exclusive), only safety assessments will be performed (See STUDY PROCEDURES). If Early Termination occurs after Day 14 (inclusive), as many Month 12/ET assessments as possible should be completed.
- 5. Follow-up visit is to take place 7 to 14 days after the last dose on Month 12 (V8).
- 6. Site eligibility review: the site will review all laboratory test results, pregnancy test, ANC and WBC, drug test results, against I/E criteria. Checklists A and B will be provided to the site by the sponsor.
- 7. Data collected at Screening for Study A841021 will be used.
- 8. Assessment results collected at Week 26 for Study A8241021 will be used for Baseline Day 1 (V2).
- 9. Single 12-lead ECG will be recorded at Baseline Day 1 (V2) and collected at Month 3 (V5), Month 6 (V6), Month 9 (V7) and Month 12/ET (V8).
- 10. Vital signs to include blood pressure, pulse and oral or tympanic body temperature.
- 11. Samples for laboratory can be obtained without regard to fasting status.
- 12. Hematology samples will be collected only for ANC and WBC safety monitoring at Week 2 (V3), Week 4 (V4) and Follow-up (V9).
- 13. Serum FSH may be performed to confirm postmenopausal status for females who have been amenorrheic for at least 12 consecutive months.
- 14. Urine Drug screen may be performed at Baseline Day 1 (V2) and any time at the discretion of the investigator.

15.**CCI**

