9. DATA ANALYSIS/STATISTICAL METHODS

Detailed methodology for summary and statistical analyses of the data collected in this study will be documented in a statistical analysis plan (SAP), which will be maintained by the sponsor. This document may modify the plans outlined in the protocol; however, any major modifications of the primary endpoint definition and/or its analysis will also be reflected in a protocol amendment.

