9.2.1. Analysis of Primary Endpoint

The primary trial variables examine long-term safety and tolerability of therapy with 20 mg BID of PF-02545920. The primary analysis of long-term safety will be focused on Adverse events, weight, vital signs (pulse, blood pressure and body temperature), physical examination, neurological examination, electrocardiogram (ECG) and clinical laboratory findings (hematology, biochemistry and urinalysis).

The endpoints are:

- The number and proportion of subjects with adverse events.
- Assessment of clinical laboratory parameters.
- Assessment of vital signs.
- Assessment of ECG parameters.
- White blood count (WBC) and absolute neutrophil count (ANC) at each visit.
- Abnormal laboratory findings from baseline.
- Frequency and severity of adverse events related to extrapyramidal symptoms (EPS) including dystonia and akathisia, as assessed by the investigator.
- C-SSRS (suicide severity assessment).

Adverse events will be coded for analysis with MedDRA[®], and the number and percent of subjects reporting each event will be summarized. Descriptive statistics will be displayed to provide an overview of the safety results. For categorical parameters, these consist of the number and percent of subjects in each category. The denominator for percentages will be based on the number of subjects appropriate for the purpose of analysis. For continuous parameters, descriptive statistics includes n, mean, standard deviation (SD), median, minimum, and maximum. Subjects who prematurely discontinued the trial will be evaluated on the basis of data collected at each visit attended.

Safety analyses will be performed on the safety population, which includes all subjects who received at least 1 dose of study medication during the open-label period.

Further information about the safety analysis can be found in Section 9.5.

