8.3. Analysis of Safety Data

8.3.1. Safety Analysis

A set of summary tables will be produced to evaluate any potential risk associated with the safety and toleration of administering PF-02545920.

The safety and other endpoints detailed here will be listed and summarized in accordance with sponsor reporting standards, where the resulting data presentations will consist of subjects from the safety analysis set. All safety endpoints will be summarized for all subjects as well as separated by three groups (ie, from PF 20mg, from PF 5mg, and from Placebo).

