8.3.9. Vital Signs

Absolute values and changes from baseline in standing, supine and postural changes for systolic and diastolic blood pressure and pulse rate will be summarized, time postdose and day, according to sponsor reporting standards. Tables will be paged by parameter.

Baseline will be defined as the predose recordings on Day 1(V2).

Maximum absolute values and changes from baseline for vital signs (for supine and standing) will also be summarized descriptively by using categories as defined in [Appendix 1](#). Numbers and percentages of subjects meeting the categorical criteria will be provided. All planned and unplanned postdose timepoints will be counted in these categorical summaries. All values meeting the criteria of potential clinical concern will be listed.

Standing vital signs will be listed only.

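### The exclusion of early-termination visits in SAP 8.1 is not limited to efficacy and, read as written, contradicts the rules for the primary safety summaries

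*SAP*

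**What the plan says.** SAP 8.1 (Statistical Methods) first assigns the safety data to the Safety population and the efficacy endpoints to the FAS. Two paragraphs on efficacy summaries, confidence intervals and plots follow. The section then responds to the study's unexpected end: "any early termination visits (ET), which occurred on and after Dec. 16th, 2016, will not be included in the summary tables and plots". It adds: "These data will be listed only". No endpoint class is named.

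Safety reporting is set out in SAP 8.3, which neither repeats the rule nor makes an exception to it. Several safety provisions point the other way:

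- SAP 8.3.1: "All safety endpoints will be summarized for all subjects as well as separated by three groups".
- SAP 6.4 defines a blood pressure endpoint as "The maximum decrease and increase from baseline over all measurements taken postdose for supine and standing systolic and diastolic blood pressures".
- SAP 8.3.9 for vital signs, and 8.3.10 for ECG in the same words: "All planned and unplanned postdose timepoints will be counted in these categorical summaries".
- SAP 8.3.8 runs the summary of new or intensified physical findings through to the Month 12/ET visit, and 8.3.6 tabulates C-CASA categories seen at any point after baseline.
- Protocol 9.2.1, on the primary endpoint: "Subjects who prematurely discontinued the trial will be evaluated on the basis of data collected at each visit attended".

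Protocol section 9 lets the SAP modify the protocol's analysis plans, but "any major modifications of the primary endpoint definition and/or its analysis will also be reflected in a protocol amendment".

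**The concern.** Long-term safety and tolerability is the primary objective, and SAP 4.1 plans no formal test of it. The descriptive tables are the primary result, so the rule that decides which visits enter them decides that result.

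The early-termination visit matters most for measures taken only a few times a year. If it is dropped, two things can happen:

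- **An earlier post-baseline value remains.** An abnormality first seen at termination disappears from the maximum and minimum changes and from the categorical tables. The number of subjects at or beyond any given threshold can then stay the same or fall, but not rise.
- **No earlier value exists.** The subject may leave both numerator and denominator, and the direction of the bias cannot be known.

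**Working it through.** The plan gives no figure that depends on this rule, so there is none to reproduce. The check compares the texts and then counts visits.

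**Texts.** Take an ECG recorded at an early-termination visit on or after 16 December 2016, while it still counts as postdose. SAP 8.3.10 puts it in the categorical table. SAP 8.1, read as written, keeps it out of every table. Both cannot be followed. The same conflict arises for supine blood pressure (6.4 and 8.3.9), physical findings (8.3.8) and C-CASA categories (8.3.6). For laboratory data and weight the SAP has no wording on all timepoints, so the conflict there rests on protocol 9.2.1.

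**Visit counts.** From the protocol's Schedule of Activities, after baseline:

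| Measure | Scheduled visits | Share held by Month 12/ET |
|---|---|---|
| Weight, chemistry, urinalysis, supine BP and pulse | V6, V8/ET | 1/2 |
| ECG | V5, V6, V7, V8/ET | 1/4 |
| ANC/WBC, C-SSRS | V3 to V9 | 1/7 |

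Standing readings are left out because 8.3.9 ends by saying they are only listed. Sitting blood pressure is taken at the other visits, but 8.3.9 does not summarise that position.

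**Earliest in-window days**, using the protocol's ±7 days: Month 6 is 182 − 7 = Day 175, and Month 3 is 91 − 7 = Day 84.

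**Loss under the literal reading**, as excluded values over scheduled values the subject has:

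- First group: terminated before the Month 6 visit, 1 of 1, leaving none; after it, 1 of 2.
- ECG: terminated before the Month 3 visit, 1 of 1, leaving none; after the Month 3, 6 or 9 visit, 1 of 2, 1 of 3 or 1 of 4.
- ANC/WBC and C-SSRS: with k visits attended from V3 to V7, then ET and follow-up, the share is 1/(k + 2). This runs from 1/2 at k = 0 to 1/7 at k = 5, but the follow-up value remains in every case.

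An unscheduled visit could supply a value that these counts do not include.

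**Not clearly affected.** SAP 6.2 defines treatment-emergent adverse events by date, up to 28 days after the last dose, so those tables do not depend on how a visit is labelled.

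**The case against.** The strongest reply is that the rule was meant for efficacy only. Within 8.1, efficacy endpoints are the only items said to be summarised and plotted, and they come just before the rule. The opening sentence on safety names only an analysis set. Section 8.3 has its own inclusion rules, and 8.3.8 keeps the termination visit in a safety summary. The SAP's version 4 change log lists 8.1 alone as affected. On this reading nothing conflicts.

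That intent is plausible, but the text does not settle it. The section covers both populations, the rule is unqualified, the log entry is unqualified too, and 8.3 is silent.

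Other points limit the impact:

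- The excluded data are still listed. So are vital-sign and ECG values of potential clinical concern, QTcF of 500 msec or more, and subjects meeting the WBC/ANC stopping criteria. Signals stay visible to a reader of listings, but listings do not correct the tables.
- SAP Appendix 3 defines visit windows for the full analysis set. If by-visit safety tables used the same windows, a termination visit at Day 120, for example, would fall between Month 3 (ending Day 98) and Month 6 (starting Day 168). It would miss those tables even without the 8.1 rule. The loss caused by the rule is therefore clearest in the maximum, minimum and categorical summaries.
- Appendix 3 opens Month 6 at Day 168, not Day 175. This moves the boundary by a week and leaves the argument unchanged.
- The 1/7 share for ANC/WBC and C-SSRS is a full-schedule figure. It is the smallest value of 1/(k + 2), and someone who stopped earlier has a larger share.

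**Conclusion.** The concern holds and should be fixed. As written, SAP 8.1 conflicts with SAP 6.4, 8.3.6, 8.3.8, 8.3.9 and 8.3.10 and with protocol 9.2.1. It leaves open which visits enter the primary safety tables. This is a defect of scope; it does not show that safety data were meant to be dropped.

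Under the literal reading, the summaries hold no scheduled post-baseline weight, chemistry, urinalysis or supine blood pressure and pulse for a subject terminated before Day 175, and no scheduled ECG for one terminated before Day 84. Subjects terminated later lose between 1 of 4 and 1 of 2 of their scheduled values for these measures. These figures assume the protocol's visit windows and no unscheduled assessments. The documents give neither the number nor the timing of terminations on or after the cut-off date, so no effect on the study population as a whole is claimed.

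**What to change.** Amend SAP 8.1 to say that the exclusion applies to efficacy summaries and plots only. State that early-termination safety data enter the laboratory, ECG, vital-sign and weight summaries, including the maximum/minimum, categorical and abnormality tables. Flag values taken after the last dose.

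If a safety exclusion really is intended, the SAP should give the reason and reconcile it with 6.4, 8.3.6, 8.3.8 to 8.3.10 and protocol 9.2.1. It should also decide whether this is a major change to the primary analysis that needs a protocol amendment, and present the safety tables with and without these visits.

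The preferred change costs one sentence and reruns of any safety tables built on the literal reading. The data are already collected and already due to be listed. The drawback is that some off-treatment values enter the tables, which is why they should be flagged.
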